2.5 Risks and Benefits

2.5.1 Potential Benefits

There are no guaranteed benefits from participation in this study; however, there are potential benefits for individuals who participate in this clinical study. Participants to be included in the present study have type 2 diabetes and have been treated with medications but still have inadequately controlled blood glucose levels. By participating in this study, participants will have an opportunity to achieve better glycemic control through a combination of structured lifestyle modification. counseling, continuous glucose monitoring, and medication monitoring in addition to the device intervention.

2.5.2 Anticipated Adverse Events Associated with the DMR Procedure

Anticipated AEs associated with the DMR procedure may include, but are not limited to, the following:

- Complications associated with upper GI endoscopy, including but not limited to, aspiration of gastric contents, aspiration pneumonia
- Complications related to sedation and anesthesia
- Cardiac or respiratory arrest during endoscopy
- Cardiac arrythmia, muscle spasm, or electrical shock during the procedure
- Death
- Duodenal mucosal inflammation, erythema, erosion, ulcer, bleeding, perforation and their associated complications
- Duodenum motility disorder
- Duodenum stricture and/or obstruction, and their associated complications or interventions
- Excess reduction in oral intake, resulting in dehydration, ketoacidosis, and their associated complications
- GI symptoms post procedure, including nasopharyngeal pain, abdominal pain, cramps, abdominal discomfort, nausea, vomiting, diarrhea, and other GI symptoms
- Inability to endoscopically remove part or all of the device, which may result in the need for surgery
- Infection, systemic or of GI tract and their associated complications

- Injury to the area of ampulla, leading to biliary and/or pancreatic complications such as biliary obstruction, pancreatitis, etc.
- Injury to peripheral tissue and their associated complications, such as peripancreatic fluid collections, pseudocyst, pancreatic and peripancreatic necrosis, peri-duodenal inflammation or abscess, vascular injuries, pseudoaneurysm, etc.
- Interfere with absorption resulting in nutritional deficiencies
- Undesired metabolic response such as hypoglycemia
- Upper GI tract trauma, including sore or irritated throat, bleeding, perforation, and their associated complications

2.5.3 Residual Risks Associated with the Investigational Device, as Identified in the Risk Analysis Report

Endogenex has conducted extensive assessment of the potential risks associated with the device and its use through Hazard Analysis and FMEA (failure mode and effects analysis) per ISO 14971. A number of safeguards have been built into the device to mitigate risks. The risk assessment concludes that, when used as intended and with mitigation measures implemented, there are no unacceptable risks to the intended patient population.

2.5.4 Risks Associated with Participation in the Clinical Investigation

There are risks associated with participation in a clinical investigation. This is an early feasibility study and therefore no clinical data with the device exists. Unanticipated adverse events associated with the device may occur. There are protocol-defined tests and follow-up studies such as endoscopy that may carry additional risk to the subjects.

2.5.5 Possible Interactions with Concomitant Medication

The effect of the DMR treatment to the absorption of orally administered medication is unknown. Published literature on DMR procedures has not reported changes in medication absorption following the DMR procedure. Participants in this study are taking glucose-lowering medications. Specific risk mitigation measures are included in the protocol, including guidelines on medication management (Section 6.2) and the use of CGM (Section 7.11) during the study.

For participants who are taking concomitant medications for other conditions, the physician should evaluate the risk and benefit of this procedure, and monitor patients closely post procedure.

2.5.6 Minimization of Risks

The following steps have been taken to further minimize the risks of the study:

- The study protocol has built in measures to control potential adverse effects, including study inclusion/exclusion criteria, staged enrollment, prophylactic medications, clinical and endoscopic surveillance, use of CGM, and guidelines for post-procedure management.
- The protocol minimizes participant's onsite visits to mitigate potential COVID-19 associated risks by allowing for a combination of virtual visits, remote monitoring, and in-home test sample collections.
- Patient informed consent contains sufficient information on the potential risks.
- Participants will be provided with study information cards that contain study and physician contact information if needed.

- Training and technical support will be provided for the DMR procedure during the study
- An DSMB will monitor the safety of the study.

In summary, participants included in the present study have a clinical indication for treatment to achieve better glycemic control. The risks associated with the device have been mitigated to the extent possible. The current study design includes additional measures to further minimize risks. These data and study design features indicate a favorable risk-benefit profile for the participants to be included in the present study.

3 STUDY OBJECTIVES AND ENDPOINTS

The objective of this FIH study is to assess the feasibility and preliminary safety of the Endogenex Device for endoscopic duodenal mucosal regeneration in individuals with type 2 diabetes inadequately controlled on 2-3 non-insulin glucose-lowering medications.

The study will also assess, as exploratory endpoints, treatment efficacy, evaluated by changes in glycemic control and liver enzymes post procedure from baseline.

Objectives	Endpoints
Primary	
To assess the safety of the Endogenex Device for DMR procedure	Proportion of participants experiencing one or more device- or procedure-related serious adverse events at 12 weeks post procedure.
Secondary	
To assess the technical feasibility of the Endogenex Device for DMR procedure	 Procedure success: defined as successful treatment of at least 6 cm of duodenum segment. Procedure time: defined as the time between the Endogenex catheter insertion and the catheter removal.
To assess changes in glycemic control	 Change from baseline in glycemic parameters post index procedure, by visits
To assess changes in liver enzymes	 HbA1c Fasting plasma glucose (FPG) Insulin-resistance by HOMA-IR Post prandial plasma glucose (PPG), Beta cell function, disposition index by mixed meal tolerance test (MMTT) Time in range, glucose variability by continuous glucose monitoring (CGM) Proportion of treated participants with an HbA1c improvement of 0.5% or more at 24 weeks from
	 Proportion of treated participants with an HbA1c improvement of 0.5% or more at 24 weeks from baseline and maintained at 48 weeks Change in weight from baseline by visit Change in glucose-lowering medication usage Change in liver enzyme from baseline at 24 weeks Alanine Aminotransferase (ALT)

	o Aspartate Aminotransferase (AST)
•	Change from baseline in blood pressure and lipid profile by visit

4 STUDY DESIGN

4.1 Study Design

This is a multicenter, open-label, treatment-only study conducted in the United States.

A total of 20 participants is planned for the study. The study will test two treatment parameters. The first 10 participants will be treated at a generator setting of 600 Volts/13 bursts/350 KHz (600V) and the second group of 10 participants at 750 Volts/8 bursts/350KHz (750V). In the 600V group, the first 5 participants will be enrolled/treated with the investigational device sequentially with at least 14 days observation time between each procedure. In the 750V group, the first participants will be enrolled/treated with the investigational device sequentially with at least 6 days observation time between each procedure.

Participants with T2D inadequately controlled on 2-3 non-insulin glucose-lowering medication(s) will be screened for study eligibility. Eligible participants who consent to participate in the study will maintain his/her background glucose-lowering medication(s) stable (no medication or dose change) for at least 12 weeks prior to baseline visit.

The index procedure will be performed under general anesthesia or deep sedation and within 21 days from the baseline visit. Participants will undergo endoscopic screening immediately prior to the DMR procedure, and eligible participants will undergo the DMR procedure. Participants may be discharged per local hospital's guideline; an overnight stay is not required but allowed per local policy and investigator's clinical judgement. A participant is enrolled in the study when the Endogenex catheter insertion is attempted. Participants excluded during endoscopic screening will be considered a screen failure and will be followed for four weeks after the procedure for safety.

Post index procedure, participants will be on a transitional diet consisting of clear liquids for 24 hours followed by a full liquid diet for 3 days, pureed food for 3 days, and soft food for one week, and then return to normal food as tolerated.

Background medication will be titrated to the pre-procedure dose and maintained for 24 weeks post index procedure and the transitional diet period per Section 6.2. After the 24-week follow-up visit, participants will be managed according to the current (2021) guidelines of the American Diabetes Association² and their glucose-lowering medications will be optimized to achieve individualized A1c goals, which for most individuals is a target of less than 7.0%.

Participants will receive lifestyle-modification counseling sessions at scheduled intervals to promote adherence to a diet and lifestyle suitable for individuals with diabetes. Counseling will be provided by a member of the research team (endocrinologist, dietitian, nurse, etc.) trained in the delivery of lifestyle counseling for diabetes.

Participants will be followed up for 48 weeks after the index procedure. The primary endpoint will be evaluated at 12 weeks post procedure.

A schematic diagram of the study design is shown in **Figure 7**.

[figure not shown]

Figure 8. Study Diagram

4.2 Participant Recruitment and Enrollment

Participants will be recruited by investigators at study sites. Potential candidates may be identified through review of hospital medical records, and/or querying an existing database, if available, and contacted by the site staff about the study. Candidates may also be recruited during routine office visits or by use of IRB-approved advertisements such as brochures, flyers, letters, digital media and other methods. Candidates who are potentially eligible for the study will be scheduled for a screening visit.

After giving written informed consent, participants will undergo screening assessments. Screening data will be reviewed to determine participant eligibility. Participants who meet all inclusion criteria and none of the general exclusion criteria will be scheduled for a baseline visit within 21 days of the planned procedure. Participants who remain eligible at the baseline visit will be scheduled for the procedure.

On the day of the procedure, participants will undergo endoscopic assessment to confirm endoscopic eligibility. Participants who meet the endoscopic eligibility will receive the DMR procedure. Participants who are excluded during endoscopic screening will be considered a screening failure and be followed for four weeks for safety.

A participant is considered enrolled in the study when the participant has given written informed consent and the Endogenex catheter insertion is attempted.

4.3 End of Study Definition

A participant is considered to have completed the study if he/she has completed all phases of the study including the last scheduled visit at week 48 in the Schedule of Activities (SoA, **Appendix 2**).

The end of the study is defined as the date of the last visit or the last scheduled procedure of the last participant in the study.

4.4 Staged Enrollment

The study will employ a staged enrollment approach to ensure participants' safety. The first group of 10 participants will be treated at 600V followed by the second group of 10 treated at 750V.

In the 600V group, the initial 5 participants will be treated sequentially with the investigational device and with a compulsory observation time of at least 14 days between each case. In the 750V group, the initial 5 participants will be treated sequentially with the investigational device and with a compulsory observation time of at least 6 days between each case. A DSMB review will be conducted after the first 5 participants have completed the treatment. Investigators should not treat additional participants until the DSMB has given the direction to do so. Based on DSMB recommendation (Section 11), enrollment of subsequent participants may occur at its natural pace without a compulsory observation time.

Additional DSMB reviews are planned at the following time as shown in **Figure 8**.

- Ten (10) participants treated and at least 5 reached the 4-week visit in the 600V group
- Five (5) participants treated in the 750V group
- All 20 participants reached the 4-week visit

[figure not shown]

Figure 9. Staged Enrollment

A safety report will be submitted to FDA after the first 5 participants in the study have completed their Week 4 visits. An additional safety report will be submitted to FDA after the first 5 participants have been treated with 750V. Enrollment may continue as described above during the submission and review period.

4.5 Stopping Rules

To protect participants' safety, stopping rules are specified as follows:

- A. Any of the following events occurring once:
 - 1) Death related or possibly related to the device or procedure
 - 2) Any device- or procedure-related event requiring intensive care unit management
 - 3) Perforation requiring radiographic/endoscopic/surgical intervention
 - 4) Refractory duodenal stricture requiring multiple dilatations (>2) or surgical intervention

- 5) Significant mucosal injury (ulcer or inflammation) with bleeding defined as (i) overt bleeding plus hemoglobin drop > 3 g/dL (provided hemoglobin drop is related to bleed). Or (ii) bleeding requiring endoscopic, radiographic or surgical treatment
- 6) Off-target tissue injury related- or possibly related to the device or procedure requiring endoscopic, radiographic or surgical treatment
- B. Other device- or procedure-related SAEs not listed above and occurring more than once.
- C. Rescue criteria invoked due to severe hyperglycemia, occurring in 2 out the first 5 participants.
- D. Severe hypoglycemia (requiring assistance of another person) occurring in 1 out of the first 5 participants.

If the stopping rule is triggered, the enrollment will be paused and a DSMB review will be conducted. Based on DSMB recommendation, Sponsor will implement necessary actions which may range from continuous monitoring, protocol modification, stopping enrollment to terminate study. Sponsor will report such events to FDA as soon as possible but no later than 10 working days after the investigator first learns of the event.

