9.3.2 Clinical Site Reporting Requirements

- All AEs and ADEs will be recorded by the investigator or designee on the eCRFs provided
- UADE or suspected UADE, or any event that can potentially trigger the stopping rules as described in Section 4.5, will be reported to the sponsor within 24 hours of knowledge of the event, followed by a written confirmation by the investigator within 5 working days
- Any other SAEs are to be reported to the sponsor within 36 hours
- The investigator at each site is ultimately responsible for reporting AEs, SAEs and UADEs to the IRB according to IRB requirements

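### Stopping rules C and D most naturally cover only the study's first five participants, all at 600V, so the 750V sentinel five have no glycemic stopping rule

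*Protocol*

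**What the plan says.** Protocol Section 4.5 lists four stopping rules. Any trigger pauses enrollment and calls a DSMB review.

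- Rule A acts on a single event from a list. For hypoglycemia the relevant items are a related or possibly related death (A1) and a related event needing intensive care (A2).
- Rule B: "Other device- or procedure-related SAEs not listed above and occurring more than once".
- Rule C: "Rescue criteria invoked due to severe hyperglycemia, occurring in 2 out the first 5 participants".
- Rule D: "Severe hypoglycemia (requiring assistance of another person) occurring in 1 out of the first 5 participants".

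Rules A and B have no participant limit. Rules C and D stop at five and name no voltage group.

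Section 4.4 treats ten participants at 600V, then ten at 750V, and sets up a sentinel five in each group. At 600V these are at least 14 days apart. For the second group it says "In the 750V group, the initial 5 participants will be treated sequentially with the investigational device", at least 6 days apart.

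Section 9.1.5 defines severe hypoglycemia as Level 3 and requires it to be reported as an adverse event; it is not automatically serious. Under Section 9.3.2, "any event that can potentially trigger the stopping rules as described in Section 4.5, will be reported to the sponsor within 24 hours", and any other SAE within 36 hours. The SAP contains no stopping rules.

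**The concern.** The protocol treats the move to 750V as a new step in exposure. It restarts sequential treatment, adds a DSMB review after five and sends FDA a further safety report. SAP Section 3 shows that the 750V group also used a second device generation. The two glycemic stopping rules do not appear to restart with it.

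The shorter spacing adds to this. The transitional diet, during which Section 6.2.2 manages hypoglycemic risk, lasts 1 + 3 + 3 + 7 = 14 days. At 6-day spacing the next 750V case can be treated while the previous participant is still in that period; at 600V the 14-day spacing roughly covers it. What is at stake is whether an early severe hypoglycemia at 750V stops the next treatment automatically or only at someone's discretion. No endpoint or estimate is affected.

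**Working it through.** The plan gives no operating figure for rules C or D, so there is none to reproduce. The check is of wording, then of what the other rules catch, then of size.

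**1. How the protocol uses the first five**

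| Place | Words | Scope |
|---|---|---|
| 4.4, first FDA report | "A safety report will be submitted to FDA after the first 5 participants in the study have completed their Week 4 visits" | study-wide, stated |
| 4.4, second FDA report | "An additional safety report will be submitted to FDA after the first 5 participants have been treated with 750V" | 750V, stated |
| 4.4, DSMB review | "A DSMB review will be conducted after the first 5 participants have completed the treatment" | unqualified |
| 4.5, rules C and D | see above | unqualified |

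Context settles the unqualified DSMB sentence. The list after it gives *additional* reviews, one of which is after five treated at 750V. The unqualified five must therefore be the earlier set, at 600V. The protocol names 750V when it means the second five. Rules C and D use the unqualified form in the very next section, so the natural reading is the study's first five.

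**2. Coverage by C and D**

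- Natural reading: 5/20 = 25% of participants; 0/10 at 750V.
- If applied per group: (5 + 5)/20 = 50%; 5/10 at 750V.

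**3. Does another rule catch one severe hypoglycemia at 750V?**

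- A1 and A2: only with death or intensive care, and only if related (for death, possibly related is enough).
- B: only if the event is a related SAE and not the first. Some severe hypoglycemia would be serious under Section 9.1.1, but a single such SAE is not enough.
- D: no, on the natural reading.

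A non-serious event, an unrelated event, or a single related SAE without death or ICU care therefore gives no automatic pause.

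**4. Effect on the 750V sequence**

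At minimum spacing the sentinel cases fall on days 0, 6, 12, 18 and 24, and the scheduled DSMB review follows the fifth. If case 1 has a severe hypoglycemia before day 6:

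- rule D per group holds back 5 − 1 = 4 sentinel cases;
- the natural reading holds back 0 automatically.

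**5. How often this would matter**

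The documents give no rate of severe hypoglycemia, so the per-participant rate p below is an assumption. Participants are taken as independent, with the same p in both groups. The chance that D triggers from one sentinel five is 1 − (1 − p)^5; from two fives it is 1 − (1 − p)^10.

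| Assumed p | D from the 750V five, per group | D at any time, natural reading | D at any time, per group |
|---|---|---|---|
| 1% | 4.9% | 4.9% | 9.6% |
| 2% | 9.6% | 9.6% | 18.3% |
| 5% | 22.6% | 22.6% | 40.1% |
| 10% | 41.0% | 41.0% | 65.1% |

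On the natural reading the chance that D triggers from the 750V five is 0 at every p.

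**6. Rule C**

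Appendix 1 requires FPG above 270 mg/dL confirmed more than 3 days later. Assume the first qualifying FPG comes on day 14, when the transitional diet ends, and count in whole days. Confirmation is then on day 14 + 4 = 18, and the second 750V participant would qualify on study day 6 + 18 = 24, when the fifth case is due. On that assumption C could rarely protect the sentinel five, though it could still hold back participants 6 to 10. Section 6.2.3 gives no start day for the FPG criterion and calls its criteria a guideline, so day 24 is illustrative.

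**The case against.** The best defense is that this is a choice, not an oversight. Confining the glycemic rules to the earliest cases is plausible, and C and D leave out participants 6 to 10 at 600V on either reading. Nothing in the documents shows that 750V with 8 bursts carries more glycemic risk than 600V with 13 bursts, and a reader should not infer that it does. Rules A and B protect all 20 participants. Sections 4.4, 10 and 11 add a DSMB review after five at 750V, ongoing and ad hoc DSMB review and medical monitoring, and Section 6.2.2 adds sulfonylurea and meglitinide dose cuts and CGM review. All of this stands and keeps the point small. None of it is an automatic pause on one event.

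Three stronger readings are tempting:

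- **That the scope is wholly unclear.** A reader might infer this because the first FDA report adds an explicit study-wide qualifier that C and D lack. That is weak evidence against the order and contrast in Section 4.4. The staged-enrollment figure was not available and could confirm or overturn the reading.
- **That a severe hypoglycemia at 750V would escape prompt reporting.** Any SAE reaches the sponsor within 36 hours whether related or not, and the 24-hour duty covers events that could *potentially* trigger a rule. What remains is a non-serious Level 3 event, on a firm study-wide reading.
- **That rule C leaves a gap of the same weight.** Its timing rests on an assumed start day, and on that assumption it would seldom act within the 750V five.

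**Conclusion.** The point holds as a minor, optional improvement. Read with Section 4.4, rules C and D cover the study's first five, so 0 of 10 participants at 750V fall under a glycemic stopping rule, against 5 of 10 if the rules ran per group. The practical gap is mainly rule D: one severe hypoglycemia at 750V, with neither death nor ICU care and not a repeat related SAE, does not automatically pause enrollment. In the worst timing, four further sentinel cases could be treated without a mandatory stop.

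This rests on the natural reading, which the unseen figure could change, and on treatment at the minimum 6-day spacing. The coverage counts need no event rate; the trigger probabilities do, and theirs is assumed.

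**What to change.** Amend rule D, and rule C for consistency, to refer to the first five participants in each voltage group, keeping the thresholds of one in five and two in five. Any DSMB charter should say the same. This takes one clause.

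The price is a higher chance of a pause and DSMB review during the 750V stage. For rule D the added chance is small if severe hypoglycemia is rare (4.9% at an assumed 1% per participant) but reaches 22.6% at 5%. If the sponsor prefers to keep the rules to the first five in the study, saying so explicitly would remove any doubt about scope, though not the gap.

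SAP Section 3 describes enrollment in the past tense, with 3 + 7 + 10 = 20 patients, which suggests that an amendment would come too late. In that case, state in the study report which scope was applied, and identify any severe hypoglycemia or severe-hyperglycemia rescue among the 750V five with the action taken. The SAP already plans to list all data and to summarize hypoglycemic events, so this adds one sentence and a short annotation.
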